### **Baseline**

Data will be collected on psychosocial factors (social support, quality of marital relationship, empowerment and functional disability, behavioral activation). We will also collect data on other socio-demographic variables including maternal age (years), maternal weight (kg), socio-economic assets (adapted from the Pakistan DHS), (44) marital status (married, single, widowed), education (years of formal education completed), and literacy (literate, semi-literate, not literate) and medically-related variables including gestational age of current pregnancy, number of pregnancies, history of SGA, LBW, PTB, stillbirth, and any complications in previous pregnancies/births. We will also collect data on current medications and current medical status, i.e. gestational diabetes, hypertension, anemia, mid-upper-arm circumference, smoking, substance abuse, and medication use for depression (though we expect these last three to be uncommon). An intimate partner violence (IPV) screening question will be administered so that referrals can be made if any women experience IPV. Women in the biological sub-study will also have their blood drawn (up to 20 mL) by a study clinician or a research assistant trained in phlebotomy. Each participant will be scheduled as close to possible to the same time of day during the morning hours for all four blood draws (as blood is drawn in HFH between 8:00am and 1:00 pm), allowing us to control for diurnal variation in cytokine levels. Blood will be collected in sodium-heparin tubes for immune cell preparation. Blood will be centrifuged within 8 hours of collection by low-density gradient centrifugation via a Z326 High Performance Centrifuge. Plasma will immediately be frozen in cryovials at -80 C in a ThermoScientific Revco RLE Ultra-Low Lab Freezer and will be stored there until it is shipped to Baltimore for analysis at the end of the trial.

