## Mediation Analysis

In order to understand the potential mediating effects of stress and social support and women's empowerment in the 3rd trimester (the primary mediators of interest) on CMDs (combined GAD and MDE) at 6 weeks postpartum, we will estimate direct and indirect (i.e. mediated) effects of the intervention using a model-based mediation package by Kosuke Imai (138). At a simple level, these mediation methods can be thought of as estimating a series of regression models, which we will use to test beliefs about the underlying process relating the mediating variables to the outcomes. Because mediation analyses depend heavily on some key identifying assumptions and the specific model forms and variables included in the models, we will do extensive diagnostics and sensitivity checks (e.g., goodness of fit tests, exploring alternative specifications and variables to be included). A benefit of the Imai et al. mediation package is that it has built-in sensitivity analyses to the key assumptions, such as that of sequential ignorability of the mediator (that the mediator values are independent of the potential outcomes, conditional on the treatment and observed covariates). All analyses within this aim will be exploratory given limited power for detecting these interaction effects and difficulties in interpreting mediational effects as causal (139).

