## Moderator Analysis

To examine potential effect modifiers of the intervention treatment effects on birth outcomes, we will expand the regression models to include a term for the interaction between intervention group status and the potential moderators (exposure to social support, stress levels, marital relationship and empowerment measured at baseline as well as retrospective report of IPV measured at 6 weeks postpartum). This will allow us to examine whether the effects of HMHB differ for mothers (or their children) with varying levels of the potential moderators; analyses will be informed by recommendations in Aiken and West (1991)(140) and Preacher et al. (2006) (141). This aim will be exploratory given limited power for detecting interaction effects.

5. **Answer the following if they are relevant to your study design:**

- If the study has different arms, explain the process for assigning participants (intervention/control, case/control), including the sequence and timing of the assignment.

Study statistician will produce a random sequence of assignments to the study arms. This sequence will be generated using a pseudo random-number generator, and will be constructed using randomly permuted blocks of size 4, 8, 12, and 16. The assignment list will be printed in order, with each step of the sequence separately stored in opaque envelopes and numbered sequentially. When an individual who has been determined as eligible via the screening procedure subsequently provides consent for study participation, the X will pull the next available envelope, opening it, and recording the assignment to intervention or control.

In addition to the participants randomized through the main study, there will be three arms for the biological study. We will choose the first 100 participants each in the intervention and control arms, and will also recruit a group of 100 healthy controls (HADS <8) who will participate only in the biological study.

- If human biospecimens (blood, urine, saliva, etc.) will be collected, provide details about who will collect the specimen, the volume (ml) and frequency of collection, how the specimen will be used, stored, identified, and disposed of when the study is over. If specimens will be collected for use in future research (beyond this study), complete the "Biospecimen Repository" section below.
-

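### Exploratory moderator and mediator analyses name baseline stress and 3rd-trimester empowerment, which the visit schedule does not provide, and use IPV reported after randomisation as a moderator

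*Combined protocol and SAP*

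**What the plan says.** The Moderator Analysis section adds arm-by-moderator interaction terms to the regression models for birth outcomes, to examine "whether the effects of HMHB differ for mothers (or their children) with varying levels of the potential moderators". It names five moderators: social support, then "stress levels, marital relationship and empowerment measured at baseline", and finally a "retrospective report of IPV measured at 6 weeks postpartum". It ends with the caveat "This aim will be exploratory given limited power for detecting interaction effects".

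The Mediation Analysis section studies the "potential mediating effects of stress and social support" and of women's "empowerment in the 3rd trimester (the primary mediators of interest) on CMDs" at 6 weeks postpartum. It carries a similar caveat: "All analyses within this aim will be exploratory given limited power for detecting these interaction effects".

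Other sections fix what these variables are. The secondary objectives in section I identify the stress moderator as self-reported perceived stress and the IPV moderator as a history of IPV. The Analysis of Secondary Efficacy Endpoint(s) section measures perceived stress with the PSS, treats the PES-Brief as a separate measure of pregnancy-related anxiety, and lists IPV among the outcomes. The Baseline section gives its psychosocial measures in one list: "Data will be collected on psychosocial factors (social support, quality of marital relationship, empowerment and functional disability, behavioral activation".

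**The concern.** A baseline moderator needs a value taken before the intervention can act on it. A 3rd-trimester mediator needs a value between randomisation and the outcome. If the forms match the schedule, two named terms have no data at the required time. The imputation foreshadowed in the Missing Data and Baseline Descriptive Statistics sections cannot supply a variable that no woman is scheduled to give at that visit. The later SAP promised under Missing Data can correct the wording but cannot create measurements. The practical risk is silent substitution: 3rd-trimester PSS standing in for baseline stress, or 6-week empowerment standing in for a mediator.

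The IPV term raises a different problem. The variable exists, but it is reported after randomisation, after the sessions and after birth. If the intervention changes disclosure, or the violence itself, then women grouped by that report are not grouped by a pre-intervention characteristic.

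**Working it through.** There is no planned figure to reproduce. The check sets the analysis text beside the schedule.

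**Step 1. Table 4, read by column** (1 screening, 2 baseline, 3 2nd trimester, 4 3rd trimester, 5 birth, 6 six weeks postpartum).

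| Measure | Columns marked | Column the analysis needs |
|---|---|---|
| PSS-10 (perceived stress) | 4, 6 | 2 (moderator) |
| Empowerment | 1, 6 | 4 (mediator) |
| DHS IPV items | 6 | pre-intervention (moderator) |
| IPV screening question | 2, 4 (then within the DHS module at 6) | not named as the moderator |
| PES-Brief (pregnancy anxiety) | 2, 4 | not a stress measure |

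**Step 2. The visit narratives.** The Baseline list contains empowerment but no stress scale. The 3rd-trimester list contains perceived stress and social support but not empowerment. Each narrative therefore shows the same gap without help from Table 4.

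**Step 3. Could a displaced column explain it?** Some rows do look displaced. The social support, marital relationship and disability scales are marked in columns 1, 3 and 6, while the narratives put them at baseline and in the 3rd trimester. So each row was tested with a shift of one column either way:

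- PSS-10: 4 becomes 3 or 5; 6 becomes 5 or 7. Column 2 is never reached.
- Empowerment: 1 becomes 0 or 2; 6 becomes 5 or 7. Column 4 is never reached. Moving only its first mark, which is what the neighbouring rows suggest, gives baseline and 6 weeks.

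**Step 4. Could another scheduled measure fill the gap?** The PES-Brief at baseline and the HADS at screening measure anxiety, not perceived stress. PSS in the 3rd trimester is itself a named mediator, so it cannot also act as a baseline moderator. Empowerment at 6 weeks is concurrent with the outcome.

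**Step 5. The IPV term.** The order of events is randomisation at enrolment, sessions in pregnancy, birth outcomes, then the IPV report at 6 weeks. IPV is a listed outcome, and section VII (plan to minimise risk B) says that parts of the programme should help address it. An arm effect on the report is therefore possible. The Missing Data section also bases subgroup analysis on baseline covariates, which sits uneasily with a 6-week moderator.

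**Count.** Moderators: 1 of 5 (stress) has no scheduled value at the named time, and 1 of 5 (IPV) is reported after randomisation. Mediators: 1 of 3 (empowerment) has no scheduled value at the named time.

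**The case against.** The strongest reply is that absence from these lists does not prove absence from the forms. The lists are incomplete elsewhere. Table 4 has no row for GAD, although SCID-diagnosed GAD is part of the primary endpoint. It marks the ASQ-3 as substudy-only, while the follow-up text gives it to all infants. The Baseline narrative omits the PES-Brief, which both Table 4 and the secondary endpoint section place at baseline. Table 4 also points to instrument descriptions in a section 8.2.3 that is not in the available text. The column test rules out a displaced mark, not an omitted one. This stands. A reader might infer that the two terms certainly cannot be run, but the documents show only that the passages conflict.

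On IPV, the text openly calls the measure retrospective, and section I speaks of history. If the recall window closes before randomisation, only disclosure could differ by arm. Both arms are screened for IPV and told where to seek care, and the 6-week assessors are masked. These points make differential reporting less likely without excluding it. The Missing Data sentence is mainly about missing covariate values, so it is weak evidence of a contradiction. A reader might infer that the IPV interaction is biased in a known direction, or that the 6-week module should simply be replaced. Neither follows: the recall window is not given, and the baseline alternative is one coarse referral question.

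Both analyses are labelled exploratory. That label excuses limited power, but not a variable with no scheduled measurement.

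**Conclusion.** The point holds as a conflict to be reconciled, of minor to moderate weight. Confidence is high that the analysis text and the schedule disagree on baseline stress and 3rd-trimester empowerment, because the narratives and Table 4 agree with each other on both gaps. Whether the data are truly missing depends on the forms, which are not in the available text. Confidence is moderate on IPV: a report made after randomisation, of something that is also an outcome, is not clean evidence of who benefits, but any bias could be negligible and its direction cannot be learned from the documents.

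A reader might infer that the trial's main result, or these aims as a whole, are compromised. They are not. The primary comparison uses none of these terms. As far as this check goes, mediation by stress and social support remains feasible, as does moderation by social support, marital relationship and empowerment.

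**What to change.** First, check the baseline and 3rd-trimester forms and correct whichever of the schedule and the analysis text is wrong. If the measures are not on the forms:

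- **Stress.** Drop baseline perceived stress from the moderators, or add PSS-10 at baseline and analyse only women who have it. Do not use PSS taken after randomisation as a moderator. Label any PES-Brief or HADS moderator as anxiety.
- **Empowerment.** Remove it from the 3rd-trimester mediators, or add the existing scale at that visit and analyse only women who have it. Do not substitute the 6-week value.

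For IPV, whatever the forms show:

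- State the recall window of the 6-week module, and label its interaction with arm as post-randomisation and descriptive.
- Report the already scheduled baseline IPV screening question alongside it as the pre-intervention moderator. First confirm that it is asked before allocation is revealed: the consent and assignment texts place both steps after consent but do not order them.

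**Cost.** Dropping terms and relabelling need only wording, which can go into the SAP before un-blinding. Adding a scale lengthens a visit and covers only later women. Section III.A describes women who had already received sessions, so enrolment had begun, and the share still to come is not given. The baseline IPV question is a single item that narrows the construct in section I and will miss exposure that the fuller module would capture. That is why it should accompany the 6-week report and not replace it.

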woman to determine if/when she has made a decision so that a separate baseline visit can be scheduled. (This will also give her the opportunity to think about it and consult with family members who are not present if she so desires before she consents.) If the first option is taken (i.e. immediate decision to participate), the staff member will conduct the baseline assessment on the same day. In both cases, the consent form with signature indicating consent to the procedures will be required before moving to baseline visit procedures.

**Who will conduct Screening Consent, Screening Procedures, and Consent for Study Participation:** HMHB members of the Assessment Team who will also be based in the hospital will ask for the potential participants' consent. These Assessment Team members will be bachelor degree graduates in social sciences, fluent in Urdu with at least one year of experience in research. They will receive training on consenting procedures and will follow standard protocol of approaching participants and providing information. As part of the consent (002 – Consent for Study Participation), the research Assessment Team will explicitly explain that the decision to participate (or to not participate) in the study will have no consequences on the usual care received by the participants and that they can withdraw their consent for participation in the study at any time without their usual care being affected.

2. How, where, and when the consent discussion(s) will occur:

Consent for Screening and Consent for Study Participation procedures/discussion will take place in a separate room or outdoor space in the presence of a nurse/ relative as a witness while taking COVID precautions. For those eligible and interested in participating, written consent will be obtained. If participant cannot read, it will be read out loud to them.

The process you will use to determine whether a potential participant meets eligibility criteria:

See subsection above title "Screening Procedures" in Section V.B.1 for full details on the screening procedures.

3. Whether you will obtain a signature from the participant or will use an oral consent process:

For both screening consent and study consent, we will obtain a signature to indicate consent, except in the case of illiterate women for whom we will obtain witnessed consent. These procedures as alternatives to written informed consent are routine and culturally acceptable in Pakistan.

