Recruitment / Consent / Randomization: Pregnant women coming for their initial prenatal visit will be screened for eligibility; this includes being “at risk” for anxiety on the anxiety subscale of the Hospital Anxiety and Depression Scale (HADS) or having moderate or high levels of anxiety (i.e. a cutoff of  $\geq$  score of 8). Informed consent will be obtained from eligible women and those agreeing to participate will be individually randomized to either the HMHB intervention or enhanced usual care (the control). A randomization sequence with varying block size (i.e. randomly permuted sizes of 4, 6, 8, and 10) will be generated by an independent researcher who is located off-site (Institute of Psychiatry, Rawalpindi, Pakistan) and is not involved in running of the study. The individual allocations will be provided to the study staff in opaque sequentially-numbered envelopes and utilized sequentially at the time of enrollment of each participant. Each woman randomized into the HMHB group will be assigned to a HMHB non-specialist provider to introduce them to the program.

Intervention Group: Women allocated to this group will receive the HMHB intervention. The content of HMHB will be based on 1) formative research (completed last year), 2) prior cognitive behavior therapy-based approaches to

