#### Follow-up (6 weeks postpartum):

The primary endpoint will be assessed at six weeks postpartum (with flexibility for -1 week and +4 week window if needed because of scheduling reasons). Women returning for their routine 6-week postpartum visit will be asked to undergo a final follow-up assessment conducted by the Assessment Team, who will be masked to the allocation status of trial participants. Women in the biological substudy will also have a blood draw (using same techniques described above under 'baseline visit'). We will also administer the *Ages & Stages Questionnaire, Third Edition (ASQ-3)* to the infants of all participants in the trial to assess infant neurobehavioral functioning.

For the detailed description of the outcomes and time points, see **Table 4** below.

In the chart below, data collection procedures that are specific to the substudy are marked as Os in the chart instead of as Xs.

Table 4: Schedule of study assessment activities

	Screening	Baseline *	2 nd trimester	3 rd trimester**	Birth	6 weeks postpartum **
	Time 1	Time 2	Time 3	Time 4	Time 5	Time 6
Informed Consent	X	X				
Eligibility assessment						
Screening step 1 (age, residence, stage of pregnancy, language)	X					
Screening Step 2 (medical exclusions)	X					
Screening Step 3 (HADS anxiety inclusion)	X					
Screening Step 4 (SCID MDE exclusion)	X					
Assessments						
Socio-demographic questions		X				
PSS-10 (stress)				X		X
PES-Brief (pregnancy anxiety)		X		X		
PHQ-9 (depressive symptoms)						X
HADS (anxiety symptoms)	X	O	O			X
HADS (symptoms of depression)	X	O	O			X
MDE diagnosis (from SCID)	X					X
MSPSS (social support)	X		X			X
MRQ (relationships)	X		X			X
Empowerment	X					X
WHO-DAS (disability)	X		X			X
DHS IPV items (violence)						X
IPV Screening Question		X		X		(in the DHS module)
PAAS (behavioral activation)		X		X		X
Breastfeeding					X	X
Parenting self-efficacy						X
PBQ (bonding)						X
MIRI (maternal responsiveness)						X
MSEQ (maternal self-efficacy)						X
Anthropometry§§						X
Economic Data						
CSRI				X		X
Blood Draw (for biology aims)	O	O	O			O
Ages & Stages Questionnaire, Third Edition (ASQ-3)						O
From medical records						
Fetal outcome: SGA in utero*				X		
Pregnancy conditions:				X		
Birth outcomes: SGA, PTB, LBW					X	
Medications	X			X		X

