The proposed study is a single-blind, individual randomized clinical trial. The assessment team, trial statistician, and PIs will be masked to allocation status of study participants. To maintain masking during the trial, intervention and assessment teams will not have any interaction during the trial, as they will be placed at separate locations within the Obstetrics Department of HFH. Furthermore, participants will be instructed not to disclose which type of treatment they are receiving to the assessment team. Fidelity of masking will be measured by having assessors guess the trial arm of each participant at the end of follow-up assessment. We hypothesize that assessors will only be able to correctly guess the condition of participants at a chance rate of nearly 50% at follow-up assessments, indicating that masking is maintained.

2. Will participants receive standard care or have current therapy stopped?

Each woman randomized into the HMHB intervention arm will receive the HMHB intervention program plus usual care. Women allocated to the control condition will get usual care (slightly enhanced) alone. The WHO recommends eight antenatal visits for positive pregnancy experience (43) which we will be the target number of visits for study participants in the control group (depending on their gestational week). These visits will involve evaluating health status, discussing any concerns, and performing routine exams consistent with stage of pregnancy. Usual care will also be enhanced by medical staff at the hospital receiving additional training in mental health treatment to counsel participants. Transportation will also be provided or facilitated for participants to assist with attending appointments and the study will pay for any ultrasounds needed.

3. Will you use a placebo or non-treatment group, and is that justifiable?

The control arm will receive a slightly enhanced version of usual care, which we consider is justifiable.

4. Explain when you may remove a participant from the study.

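### The envelope is opened on study consent by an unnamed person, with no requirement that baseline be finished first and nothing keeping the outcome assessors away from that step

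*Combined protocol and SAP*

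**What the plan says.** **Trigger and opener.** The item on assigning participants to arms (Section V, item 5) makes study consent by an eligible woman the trigger. At that point "the X will pull the next available envelope, opening it, and recording the assignment to intervention or control". X stands where a role should be. It is ordinary text and not one of the marks used for removed names.

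**Second description.** Under Study Implementation, the Recruitment / Consent / Randomization paragraph reads: "The individual allocations will be provided to the study staff in opaque sequentially-numbered envelopes and utilized sequentially at the time of enrollment of each participant". It does not say which staff.

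**Consent and baseline.** Section V.B says "HMHB members of the Assessment Team who will also be based in the hospital will ask for the potential participants' consent". A signed consent form is required before any baseline procedure. If the woman decides at once, "the staff member will conduct the baseline assessment on the same day". If she wants time, a separate baseline visit is arranged.

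**Outcome assessment.** At six weeks postpartum there is a "final follow-up assessment conducted by the Assessment Team, who will be masked to the allocation status of trial participants". The primary outcome is SCID-diagnosed GAD and MDE (Analysis of Primary Efficacy Endpoint(s)).

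**Masking.** The answer on staff blinding in Section V, item 5 states: "The assessment team, trial statistician, and PIs will be masked to allocation status of study participants". It adds three safeguards: the intervention and assessment teams are kept apart, women are told not to reveal their arm to assessors, and assessors guess the arm at the end of follow-up.

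**The concern.** Two things depend on this step.

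The first is the order of allocation and baseline. The women are not masked. If a woman, or the person interviewing her, already knows her arm, self-reported baseline measures can be coloured by it. Those measures supply the moderators (social support, marital relationship, empowerment) and the adjustment variables in the sensitivity regressions. A covariate collected after allocation is known is no longer guaranteed to be independent of arm.

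The second is the masking of the primary outcome. The SCID is an interviewer's judgement, and the team that makes it at six weeks is also the team with the woman when she consents, which is the event that triggers the envelope. A statement that the team is masked needs a procedure behind it. At this step the person who would make it checkable is not identified.

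**Working it through.** **1. Order of events**

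| Event | What the plan fixes | Where |
|---|---|---|
| HADS and SCID depression screen | Before study consent | V.B, Screening Procedures |
| Study consent | Taken by the Assessment Team | V.B |
| Envelope opened, arm recorded | On consent (item 5) or at enrolment (Study Implementation); by X or by unspecified study staff | V, item 5; Study Implementation |
| Baseline assessment | After signed consent; same day or at a later visit | V.B |
| Six-week assessment | By the Assessment Team, stated to be masked | Follow-up |

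The envelope and the baseline assessment both follow consent, and neither is placed relative to the other. Under item 5 consent is the only condition for opening, so opening before baseline complies with the text.

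**2. Do the stated safeguards reach the envelope step?**

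- Team separation keeps assessors away from those who deliver HMHB. It says nothing about who holds or opens envelopes.
- Participant non-disclosure limits leakage from the woman after allocation, not from the envelope or the assignment record.
- The assessor guess can detect lost masking at the end. It does not prevent it.

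None of the three covers the step.

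**3. The plan's own figure**

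This point contests no number, but the illustration in step 4 uses the sample-size inputs, so I reproduced them first. From Section III.B: control prevalence 0.30, a 30% relative reduction to 0.21, 85% power, 1:1 allocation. The paragraph gives no alpha for the main trial; I assume two-sided 0.05.

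n = [1.960·√(2·0.255·0.745) + 1.036·√(0.30·0.70 + 0.21·0.79)]² / 0.09² = (1.208 + 0.635)² / 0.0081 ≈ 419.6, so 420 per arm. 840 / 0.70 = 1200. Both agree with the plan.

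**4. Hypothetical illustration of what lost masking could do**

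Assume no true effect: true prevalence 0.30 in both arms, 420 per arm. Assume also that rating lowers recorded caseness in the HMHB arm by d. The size of d is my assumption; the documents give no value.

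P(significant) = Φ((d − 1.96·s₀)/s₁) + Φ((−d − 1.96·s₀)/s₁), where s₀ = √(2·p̄·(1−p̄)/420) and s₁ = √((0.21 + p₂(1−p₂))/420), with p₂ = 0.30 − d and p̄ the mean of 0.30 and p₂.

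For d = 0.03: p₂ = 0.27, s₀ = 0.03115, s₁ = 0.03113. This gives Φ(−0.998) + Φ(−2.925) = 0.159 + 0.002 = 0.161.

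For d = 0.05: p₂ = 0.25, s₀ = 0.03081, s₁ = 0.03076. This gives Φ(−0.338) + Φ(−3.589) = 0.368.

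The Fisher column comes from exact enumeration over all tables with 420 per arm.

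| Assumed shift | Chi-square | Fisher (the planned test) |
|---|---|---|
| 0 | 5.0% | 4.2% |
| 1.5 points | 7.7% | 6.6% |
| 3 points | 16.1% | 14.4% |
| 5 points | 36.8% | 34.0% |

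**The case against.** A reader might infer that, because the Assessment Team takes consent and consent triggers the envelope, the masked raters can see allocation. The documents do not support that. No section has this team hold, open or watch an envelope. Section V.B gives it screening and consent, not randomization. Item 5 gives the opening to a separate, unnamed actor, and two places state that the team is masked. The reading most consistent with the whole text is that X is someone else. The plan also mentions a study coordinator, a data manager and a trial manager, so it does not follow that assessors are the only staff who could do it.

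A reader might also say that assessor masking is the trial's only blinding. It is not: the trial statistician and the PIs are masked too, and the analysis plan is to be final before unblinding.

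On baseline order, the text leaves the sequence open; it does not put the envelope first. Screening HADS and the SCID depression screen come before study consent, so allocation cannot affect them. Fisher's exact test takes no covariates, so baseline values enter the sensitivity and moderator models and not the primary test. Table 4, in the copy I worked from, shows the social support, relationship and empowerment scales under screening. Its columns may be displaced, and the Baseline and Moderator Analysis text puts these measures at baseline. If the table is right, fewer measures are exposed.

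The illustration applies the shift to the whole HMHB arm, as if every rater knew each woman's arm and remembered it from 22 weeks' gestation or earlier to six weeks postpartum. If half the arm were affected by a 3-point shift, the average shift would be 1.5 points and the rate 6.6–7.7%.

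All of this stands. It narrows the point but does not remove it: the order is not fixed, the opener is not named, and no safeguard covers the step.

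**Conclusion.** The point holds as a gap in procedure. Followed literally, the consent trigger lets allocation be known before baseline covariates and moderators are collected. The stated masking of the outcome assessors is not assured at the envelope step, because the opener is unidentified and the Assessment Team is not excluded. There is no evidence in the documents that assessors see allocation, and I do not conclude that they do.

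The size is unknown. The false-positive rates in the working rest on an assumed rating shift, an assumed alpha of 0.05, and the plan's own 30% prevalence and 420 per arm. They show only that a shift of a few points would matter if it occurred. The sample size and the planned analyses are unaffected. I would class this as a cheap improvement worth making, not as an error in the plan as written.

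**What to change.** 1. In Section V, item 5 and in the Recruitment / Consent / Randomization paragraph, change the trigger: the envelope is opened only after study consent is signed and the baseline assessment is complete and logged.
2. Replace X with an existing role outside both the Assessment Team and the intervention team, for example the study coordinator. A member of the HMHB team would be a poor choice, because the hand-off from assessors would conflict with the rule that the two teams do not interact.
3. State that Assessment Team members never hold envelopes or see the allocation record, and say who keeps that record.

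The same edit should reconcile the two accounts of the sequence. One has an independent off-site researcher and blocks of 4, 6, 8 and 10. The other has the study statistician and blocks of 4, 8, 12 and 16, while the trial statistician is said to be masked.

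**Cost.** Protocol wording, a role assignment, and a short hand-off after baseline. Women who consent but do not complete baseline will not be randomized, so they should be counted in the participant flow. The documents give no staffing numbers, so whether the coordinator can cover every enrolment needs to be confirmed on site.
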